All 42 subjects enrolled completed the study. GM-CSF was not measurable in serum before study drug administration. In the SAD part, GM-CSF was absorbed into systemic circulation with t_{max} of 2 hours after inhalation of molgramostim nebuliser solution, however, at picogram levels 50-100 times lower than has been observed after similar doses of sargramostim administered intravenously. Total systemic exposure (AUC_{last}) increased with dose ranging between 13 and 138 pg•h/mL and C_{max} ranged between 9.1 and 41 pg/mL (C_{max} was similar for the 300 and 600 µg dose levels). In the MAD part, despite the short half-life of approximately 4 hours where GM-CSF levels returned to levels below quantification limits after each dose, there was evidence of some accumulation after multiple dosing. C_{max} increased from 32 pg/mL on Day 1 to 90 pg/mL on Day 6 for the 300 µg dose level and from 96 pg/mL to 251 pg/mL from Days 1 to 6 for the 600 µg dose level. Likewise AUC_{last} increased from 97 to 248 pg•h/mL from Days 1 to 6 for the 300 µg dose level and from 350 to 802 pg•h/mL for the 600 µg dose level. Minimum measurable plasma concentrations (C_{min}) on Day 6 were 3.6 and 5.1 pg/mL measured at 8 and 12 hours, respectively for the 300 and 600 µg dose levels.

Changes in white blood cells (WBC) and differential counts were in-line with the mode-of-action of GM-CSF and these were not clinically significant in most subjects. In subjects treated with molgramostim nebuliser solution a slight increase in total WBC and differential counts (primarily within normal reference ranges) was observed in a dose-dependent manner. Two subjects had adverse events (AEs) concerning WBC differential counts that were considered related to GM-CSF (eosinophilia and white blood cell count increased). Additionally, inhalation of molgramostim nebuliser solution resulted in increases in exhaled fraction of nitric oxide (FeNO) compared with placebo.

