7.2.1.4 Week 4 (Visit 3)

TIME WINDOW:

28 days (± 7 days) after Randomisation (Visit 2)

ACTIVITIES AND ASSESSMENTS:

At Week 4 (Visit 3), the following activities and assessments will be performed:

- Concomitant medication (*Section 10.3.3*)
- Physical examination (*Section 10.4.3*)
- Vital signs (*Section 10.4.4*)
- (A-a)DO₂ and PaO₂ (*Section 10.1.1*)
- Lung function tests (*Section 10.1.2*)
- 6MWT (*Section 10.1.3*)
- Dyspnoea score (*Section 10.1.4*)
- Cough scores (*Section 10.1.5*)
- QoL score (*Section 10.1.7*)
- Serum pregnancy test (*Section 10.5*)
- Laboratory safety assessments (haematology and clinical chemistry) (*Section 10.4.6*)
- Biomarkers and GM-CSF prior to administration of trial drug in clinic (*Section 10.1.9*).
- Anti-drug antibodies prior to administration of trial drug in clinic (*Section 10.1.9*)
- AEs (*Section 10.4.2*)
- Subject Diary Card (*Section 10.4.2*)
- Treatment compliance (*Section 9.5*)
- Administration of trial drug at the site (*Section 9.1.5*)
- Dispense trial drug (*Section 9.1.4*)
- Sample for GM-CSF two hours after completion of administration of trial drug (*Section 10.1.9*)

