9 TREATMENT OF SUBJECTS

9.1 Investigational Medicinal Products

9.1.1 Treatment Regimens

Subjects will be randomised to receive double-blind treatment for up to 24 weeks with either:

- inhaled molgramostim (300 µg) administered once daily,
- inhaled molgramostim (300 µg) and matching placebo administered intermittently (12 cycles of seven days molgramostim followed by seven days placebo; both administered once daily) or
- inhaled placebo administered once daily.

In the Follow-up period all subjects will receive treatment with inhaled molgramostim (300 µg) administered intermittently (12 or 24 cycles of seven days molgramostim followed by seven days off-treatment) for 24 or 48 weeks. For subjects who entered the Follow-up period before Amendment 11 was approved by the national authorities, treatment with molgramostim in the Follow-up period is not mandatory.

Treatment with molgramostim in the Follow-up period should be discontinued in case of disease worsening and/or safety concerns.

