9.1.3 Manufacturing, Packaging and Labelling of Investigational Medicinal Product

All manufacturing and packaging will be performed in accordance with current Good Manufacturing Practice (GMP).

Individual medication kits containing double-blind trial medication for one week will be supplied in adequate amounts at the dispensing visits. Every kit will be labelled with a unique medication number, which also appear on a tear-off part of the label.

Labels will comply with local regulations and will be printed in local language.

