9.1.5 Investigational Medicinal Product Administration and Training

The PARI eFlow nebuliser system (PARI Pharma GmbH, Germany) will be used to administer the IMP. The eFlow Nebuliser Handset is a single subject use, reusable electronic nebuliser. It includes a fine particle aerosol generator (perforated vibrating membrane) defined by a 30L mesh and an aerosol chamber that can produce aerosols with high density of active drug, precisely defined droplet size and a high proportion of respirable droplets.

All subjects, investigators and trial nurses will be trained in IMP administration and medical device maintenance procedure. The training of the subjects will be arranged prior to administration of the subject's first dose of IMP and checked in clinic on first dosing. The subject will also receive written instructions.

The subject will administer the first dose of IMP post randomisation at the Baseline visit (Visit 2) under the supervision of trial personnel.

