9.5 Treatment Compliance

Subject compliance in the Double-blind treatment and Follow-up periods will be evaluated by unused and used vial counts. Subjects will be asked to return all unused and empty vials at the next clinic visit. Vials will be visually inspected for opening. The number of unused and empty vials will be counted upon return and recorded in the drug accountability log kept at the site. To verify correct treatment in the Double-blind period the subjects will apply the tear-off label from the weekly kit in the Diary Card (see Section 10.4.2).

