Similar summaries will be done for double-blind treatment period and the Follow-up period.

Change in serum concentration of GM-CSF post first dose of trial drug and after 4-weeks treatment

Pre and 2h post dose serum concentration of GM-CSF, and the corresponding changes (2h post dose measurement – pre dose measurement) will be summarised for first dose of trial drug and after 4 weeks of treatment.

In US sites, additional sampling is done 12 and 24 weeks after randomization, and at week 12 during follow-up, including pre and 2h post dose. These US sampling data will be summarised separately, in the same way as described above.

For sites in Japan additional sampling is done, including pre-dose and samples at 1, 2, 4 and 8 hours post dose. These sampling profiles for Japan will be summarised separately. If applicable (sufficient number of samples have GM-CSF concentrations above LLOQ) standard PK parameters will be derived and evaluated, and the results will be provided in a separate PK-report.

Number of subjects in need for oxygen supplement therapy

Number of subjects in need for oxygen supplement therapy, will be summarised by visit during 24-weeks treatment. The number of subjects in need for oxygen supplement therapy will be defined based on actual use of oxygen supplementation as recorded in concomitant therapy. Oxygen therapy will be summarised separately according to start and stop date of therapy, in the same way that other concomitant medication is presented. Proportion of subjects with supplemental oxygen therapy will be compared between treatment groups using a logistic regression model including treatment, baseline use of supplemental oxygen therapy, strata, and Japan vs Other countries.

The distribution of DSS at Screening and at Week 24

Shift tables will be produced for observed DSS scores at Screening/Baseline vs Week 24, displaying both the visit distributions and the shifts between visits. Similar shift tables will also be produced displaying number of subjects with a DSS score of 1 or 2, vs number of subjects not reaching a DSS score of 1 or 2.

Follow-up period

The following endpoints related to visits in the follow-up period will be summarised, both by randomised treatment during the double-blind treatment period and in total, in the same way that the corresponding endpoints during the double-blind treatment period is summarised.

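### In the intermittent arm, the Week 4 GM-CSF summary (and the US Week 12 summary) may mix samples taken after active and after placebo doses, and the SAP does not separate them

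*SAP*

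**What the plan says.** SAP 5.3.8, on change in serum GM-CSF, plans the pre-dose value, the 2 h post-dose value and post minus pre. These "will be summarised for first dose of trial drug and after 4 weeks of treatment". Exploratory endpoints in that section are shown by visit and treatment group. The additional US samples at Weeks 12 and 24 are handled the same way, and Japan's repeated post-dose samples are summarised separately. In SAP Appendix 1, the titles of Tables 14.2.4.17 (all sites), 14.2.4.18 (Japan) and 14.2.4.19 (US) name no split by what the dose contained.

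The protocol fixes the dosing calendar. Section 9.1.1 gives the intermittent regimen as "12 cycles of seven days molgramostim followed by seven days placebo; both administered once daily". Section 9.1.5 starts it in the clinic: "The subject will administer the first dose of IMP post randomisation at the Baseline visit (Visit 2) under the supervision of trial personnel". Section 7.2.1.4 places Week 4 at 28 days after randomisation, plus or minus 7, with a dose given at the site and then: "Sample for GM-CSF two hours after completion of administration of trial drug".

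On supply, section 9.1.3 says: "Individual medication kits containing double-blind trial medication for one week will be supplied in adequate amounts at the dispensing visits". Section 9.5 adds: "To verify correct treatment in the Double-blind period the subjects will apply the tear-off label from the weekly kit in the Diary Card".

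No passage ties the Week 4 visit to an active week, says whether the clinic dose comes from the kit in use or a newly dispensed one, or asks for the sample to be labelled by dose content.

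**The concern.** The exploratory objective is the effect of molgramostim on serum GM-CSF after the first dose and after 4 weeks. A 2 h post-dose sample informs that objective only if the dose was molgramostim. In the intermittent arm, a patient seen on schedule at Week 4 may have inhaled placebo in the clinic, and the SAP would average that sample with those taken after molgramostim.

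The mean and the post-minus-pre change for that arm would then depend partly on how many visits fell in a placebo week. Set beside the once-daily arm in the same table, a lower Week 4 value could be read as a difference between regimens when part of it is visit timing.

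**Working it through.** **Inputs.** Regimen: 7 active days, then 7 placebo days, 12 cycles (Protocol 9.1.1). First dose at Baseline after randomisation (Protocol 9.1.5), taken as Day 1. Visit windows of ± 7 days around 28, 84 and 168 days (Protocol 7.2.1.4, 7.2.1.6, 7.2.1.9). Phase I figures from Protocol 5.1.

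**Check of the calendar.** 12 × 14 = 168 days = 24 weeks, which matches the planned double-blind period.

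**Rule.** Day d is an active day if (d − 1) mod 14 is below 7, and otherwise a placebo day.

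**Week 4.** 28 days after Day 1 is Day 29, so the window is Days 22 to 36:
- Days 22 to 28: placebo (7 days)
- Days 29 to 35: active (7 days)
- Day 36: placebo (1 day)

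That is 8 placebo and 7 active days out of 15. The nominal Day 29 is the first active day of cycle 3, and a visit one day earlier falls on a placebo day. If the visit is counted instead as study Day 28, the window is Days 21 to 35, with 7 placebo and 8 active days, and the nominal day is the last placebo day. Under either count both dose types lie in the window and the nominal visit sits at the switch.

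**US Week 12.** Nominal Day 85, window Days 78 to 92: the same pattern, 8 placebo and 7 active days.

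**US Week 24.** Nominal Day 169, window Days 162 to 176. Days 162 to 168 are the last placebo week. The twelve cycles then end, so no double-blind dose is scheduled from Day 169. Protocol 9.1.4 dispenses double-blind kits at Visits 2 to 7 and unblinded kits at Visit 8, where Protocol 7.2.1.9 also lists a clinic dose. The ambiguity there is double-blind or open-label supply, and it applies to all arms.

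**Size, as an illustration.** In phase I the half-life was about 4 hours and "GM-CSF levels returned to levels below quantification limits after each dose". At 300 µg the mean peak was 32 pg/mL on Day 1 and 90 pg/mL on Day 6. Assume that these levels carry over to aPAP and to the 2 h sample, and that a post-placebo value is about zero. With p the share of placebo-dose samples and m the active-dose mean:

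pooled mean = (1 − p) × m; SD added by mixing alone = m × √(p(1 − p))

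| p | mean, m = 32 | mean, m = 90 | added SD, m = 32 | added SD, m = 90 |
|---|---|---|---|---|
| 0 | 32 | 90 | 0 | 0 |
| 0.25 | 24.0 | 67.5 | 13.9 | 39.0 |
| 7/15 | 17.1 | 48.0 | 16.0 | 44.9 |
| 0.50 | 16.0 | 45.0 | 16.0 | 45.0 |
| 8/15 | 14.9 | 42.0 | 16.0 | 44.9 |

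The share p is not known. The value 8/15 counts permitted days; it is a share of samples only if visits spread evenly over the window.

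**The case against.** **Nothing is pooled across arms.** A reader might infer that the GM-CSF results as a whole cannot be interpreted. The documents do not support that. Summaries are by treatment group, the once-daily and placebo arms each have one dose type at Week 4, and the intermittent cycle starts with active drug, so first-dose summaries are clean in every arm. The objective can still be addressed from the first dose in both active arms and from Week 4 in the once-daily arm. This stands and limits the point to one arm.

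**Mixing is not established.** Kits hold one week of drug, and Week 4 is also a dispensing visit. If the clinic dose always came from a new kit that starts a cycle, every Week 4 dose could be active. This stands too: mixing is possible, not certain. But the documents do not state such a rule, and a split by the kit actually used would settle the question.

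**The concentrations are borrowed.** They are peaks in healthy volunteers. Patients here carry neutralising autoantibodies to GM-CSF, and the SAP makes the Japanese PK evaluation conditional on enough samples being above the lower limit of quantification. The table above therefore shows direction and scale and is not a forecast.

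**It can be recovered.** GM-CSF values, treatment allocation and visit dates are listed individually, and the endpoint is descriptive. That is true, but the listings are not described as showing dose content, and visit date alone does not identify the kit used.

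**Conclusion.** The point holds as a minor one. On the protocol's own calendar, the intermittent arm's Week 4 window contains 7 or 8 placebo days out of 15, depending on how days are counted, and the nominal visit falls at the switch. The SAP does not classify the samples. Unless the clinic dose always comes from an active kit, that arm's Week 4 summary, its part of the Japan profiles and its US Week 12 summary may be mixtures of unknown proportion. If phase I behaviour carries over to aPAP, post-placebo samples would lie near the quantification limit, so mixing would lower the mean in proportion to the placebo share and widen the spread.

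It would be wrong to read this as a defect in all the GM-CSF data, or as proof that about half of the samples followed placebo. US Week 24 is a separate question about double-blind or open-label supply.

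**What to change.** Write the classification rule into the pre-analysis review document (SAP 5.2) before unblinding, and apply it afterwards:

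- **Week 4 (including the Japan profiles) and US Week 12, intermittent arm:** flag each sample as active-dose or placebo-dose according to the kit used for the clinic dose, from the IWRS kit number, the Diary Card tear-off label and the visit date. Where these do not settle it, record the sample as undetermined. Present the active-dose and placebo-dose subsets separately, with n for each and the number undetermined.
- **US Week 24, all arms:** flag whether the clinic dose came from double-blind or open-label supply, and present the results by that flag.

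The cost is one derived variable and a few extra table rows. Some kit reconciliation may be needed: the protocol says that adverse events from the Diary Card go to the eCRF but does not say that kit labels do, and the IWRS is described as assigning kits at dispensing visits, not as recording which one supplied the clinic dose. The subsets will also be smaller. With the planned 45 patients per arm and an even spread over the window, Week 4 would split into about 24 placebo-dose samples (45 × 8/15) and 21 active-dose samples (45 × 7/15), and the Japan and US subsets would be smaller still. No new samples or visits are needed.

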7.2.1.2 Screening (Visit 1)

ACTIVITIES AND ASSESSMENTS:

At Screening (Visit 1), the following activities and assessments will be performed:

- Informed consent (if not done during pre-screening visit period, *Section 7.2.1.1*) - Signed and dated by the subject and by the person who conducted the informed

consent discussion will be collected prior to any trial related procedures described in this protocol (*Section 13.1.3*)

- Eligibility criteria - Assessment of inclusion and exclusion criteria (*Section 8.2* and *Section 8.3*)
- Demographics and Baseline data (*Section 10.3.1*)
- Medical history (*Section 10.3.2*)
- Physical examination (*Section 10.4.3*)
- Vital signs (*Section 10.4.4*)
- (A-a)DO₂ and PaO₂ (*Section 10.1.1*)
- Lung function tests (*Section 10.1.2*)
- 6MWT (*Section 10.1.3*)
- Laboratory safety assessments (haematology and clinical chemistry) (*Section 10.4.6*)
- Serum pregnancy test and instruction in contraceptive measures (*Section 10.5*)
- DSS (*Section 10.1.8*)
- Arrangement for trial drug administration training (*Section 9.1.5*)

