10 TRIAL ASSESSMENTS

10.1 Efficacy Assessments

10.1.1 Blood Gas Analysis

The following variables will be assessed from an arterial blood gas sample at the timepoints shown in *Table 1*:

- (A-a)DO₂ (mmHg/kPa)
- PaO₂ (mmHg/kPa)
- PaCO₂ (mmHg/kPa)

Sites that are experienced in the use of capillary sampling for blood gas analysis as part of their standard care, may use this option instead of an arterial blood gas sample at Screening (Visit 1), Weeks 4 and 12 (Visits 3 and 5) and all Follow-up Visits, but an arterial sample for blood gas is mandatory at Baseline (Visit 2) and Week 24 (Visit 8).

Subjects should rest for at least 10 minutes before puncture and the sample should be taken in supine position. Trial specific instructions will be provided in a separate document. The sample will be analysed in accordance with local routines.

If possible, arterial blood gases at Baseline should be conducted with the subject breathing room air. If the subject cannot tolerate temporary discontinuation of supplemental oxygen during blood gas sampling at Baseline, blood gas sampling at subsequent visits should be conducted using the same oxygen flow rate as was used at Baseline.

The (A-a)DO₂ will be calculated based on PaO₂, PaCO₂ and the ambient atmospheric pressure based on a standard equation (see section 10.2.1).

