10.1.8 Disease Severity Score

The DSS will be assessed at the timepoints shown in *Table 1*.

The DSS is based on the presence of symptoms and degree of reduction in PaO₂ determined with the individual breathing room air in the supine position [37].

The DSS is a 5-point score as follows:

- 1 = no symptoms and PaO₂ ≥ 70 mmHg
- 2 = symptomatic and PaO₂ ≥ 70 mmHg
- 3 = 60 mmHg ≤ PaO₂ < 70 mmHg
- 4 = 50 mmHg ≤ PaO₂ < 60 mmHg
- 5 = PaO₂ < 50 mmHg.

If possible, the blood gas assessment should be conducted with the subject breathing room air (see 10.1.1). For subjects requiring supplemental oxygen during the blood gas assessment the DSS will be based on the PaO₂ obtained while breathing oxygen.

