10.2.3 Exploratory Endpoints

10.2.3.1 Double-Blind Treatment Period

- Absolute change from baseline of (A-a)DO₂, VC (% predicted), DLCO (% predicted), FEV₁ (% predicted), FVC (% predicted), and relative change from baseline of PaO₂ after 4 and 12-weeks, treatment
- Time period during which the (A-a)DO₂ level is maintained below Baseline –10mmHg
- Number of subjects with improved tolerance to exercise (increase in distance walked ≥ 50 m or desaturation <4 percentage points on the 6MWT) after 4 and 12-weeks treatment
- Time period during which the improvement in tolerance to exercise is maintained
- Change from baseline in dyspnoea score and cough scores after 4 and 12-weeks treatment
- Number of subjects with improved QoL (change of ≥4 units on the SGRQ/number of subjects with 'no problems' in the EQ-5D-5L), after 4, 12, and 24-weeks treatment
- Change in serum concentration of biomarkers; KL-6, CEA, SP-A, SP-B, SP-C, SP-D, Cyfra 21-1 and LDH after 4, 12, and 24-weeks treatment
- Levels of anti-GM-CSF after 4, 12 and 24-weeks treatment
- Change in serum concentration of GM-CSF post first dose of trial drug and after 4-weeks treatment
- Number of subjects in need for oxygen supplement therapy during 24-weeks treatment
- The distribution of DSS at Screening and at Week 24
- The percentage of subjects with DSS 1 or 2 at Week 24

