3 OVERALL STUDY DESIGN

3.1 Overview of Study Design

[figure not shown]
This is a parallel, double-blind, multicentre, randomised clinical trial in autoimmune pulmonary alveolar proteinosis subjects, where a planned total of 135 subjects (see section 3.2) are stratified according to whether or not a WLL has been conducted within 2 months prior to the Baseline (according to protocol version 4.0 and later versions), or whether or not

WLL was conducted between the screening visit and the randomization visit (according to protocol versions before version 4.0). Subjects will be randomised 1:1:1 to receive treatment for up to 24 weeks with either;

- 1) Inhaled molgramostim (300 µg) administered once daily,
- 2) Inhaled molgramostim (300 µg) and matching placebo administered intermittently (12 cycles of seven days molgramostim, seven days placebo; both administered once daily) or
- 3) Inhaled placebo administered once daily.

The trial includes two phases; a Double-blind treatment period consisting of up to eight trial visits (Screening, Baseline, and at Weeks 4, 8, 12, 16, 20 and 24 after randomisation) and a Follow-up period consisting of up to five trial visits (at Weeks 4, 12, 24, 36 and 48 post-treatment). During the follow-up period all subjects recruited under protocol version 4.0 or later versions will receive treatment with inhaled molgramostim (300 µg) administered once daily in an intermittent regimen for 24 weeks (12 cycles of seven days molgramostim, seven days off). Patients recruited under protocol version 2.0 were only to receive treatment in the follow-up period in case of worsening of aPAP, and patients recruited under protocol version 3.0 were treated (if needed) using the intermittent regimen for 24 weeks and according to investigator’s discretion for 24 additional weeks. Likewise, the 36 and 48-weeks post treatment visits are only applicable for subjects included before approval of protocol version 4.0.

Figure 1 Overall Trial Design

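### Where the capillary option is used at Screening, the within-arm DSS shift to Week 24 compares a capillary with an arterial PaO₂, although an arterial Baseline PaO₂ is mandated

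*SAP*

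**What the plan says.** - **Comparison.** SAP 5.3.8: "Shift tables will be produced for observed DSS scores at Screening/Baseline vs Week 24". It does not say which blood gas feeds the first score. The protocol endpoint (10.2.3.1) is "The distribution of DSS at Screening and at Week 24", and the titles of Tables 14.2.4.22 to 14.2.4.25 in SAP Appendix 1 also name Screening and Week 24.
- **Score.** Protocol 10.1.8: "The DSS is based on the presence of symptoms and degree of reduction in PaO₂". The middle class, for example, is "3 = 60 mmHg ≤ PaO₂ < 70 mmHg". PaO₂ alone sets classes 3, 4 and 5; symptoms only separate class 1 from class 2.
- **Visits.** DSS is in the Screening list (Protocol 7.2.1.2) and the Week 24 list (7.2.1.9). It is absent from the Baseline list (7.2.1.3) and has no Baseline mark in Table 1.
- **Sample type.** Protocol 10.1.1: sites experienced in capillary sampling "may use this option instead of an arterial blood gas sample at Screening (Visit 1"), whereas "an arterial sample for blood gas is mandatory at Baseline (Visit 2) and Week 24 (Visit 8").
- **Subgroups.** SAP 5.8, Table 2, defines aPAP severity as DSS 2/3/4/5 for the primary and key secondary efficacy endpoints, among others. It does not name the visit of that DSS.
- **Sample type elsewhere.** For follow-up (A-a)DO₂, SAP 5.3.8 adds a summary restricted to arterial samples (Table 14.2.5.6). There is no such rule for DSS.

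**The concern.** A subject screened with capillary blood has a capillary score before treatment and an arterial score after it. If the two sample types differ systematically, part of the tabulated shift reflects the sample and not the patient. The bands are only 10 mmHg wide, so an offset of a few mmHg can move many subjects across a cut-off. A reader of the shift tables, or of the percentages with DSS 1 or 2, would see movement within each arm and could take it for improvement or worsening on treatment.

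The severity subgroups have a smaller version of the problem. If Screening DSS defines them, some subjects carry a label that depends on how their blood was drawn.

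Both are avoidable, because the protocol requires an arterial PaO₂ at Baseline and the plan does not clearly use it for DSS.

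**Working it through.** The plan gives no power, sample size or expected value for DSS, so there is no figure to reproduce. The check has two parts.

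**1. Schedule against sample rule (from the documents)**

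| Visit | DSS scheduled | Blood gas |
|---|---|---|
| Screening (Visit 1) | yes | arterial, or capillary by site routine |
| Baseline (Visit 2) | no | arterial mandatory |
| Week 24 (Visit 8) | yes | arterial mandatory |

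The designed pair is therefore Screening to Week 24, and only its second member is certain to be arterial.

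**2. Possible size (assumed inputs)**

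The documents do not give the capillary-minus-arterial offset, its sign, the share of capillary samples or the PaO₂ distribution. Assumed:

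- true PaO₂ normal with mean 65 or 70 mmHg and SD 9, unchanged over 24 weeks;
- within-subject SD 4 at each visit;
- offset b from −6 to +6 mmHg at Screening only;
- capillary share s of 10% to 50%.

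The cut-offs are the protocol's. Net spurious shift = P(class better at Week 24) − P(class worse at Week 24), simulated with 2,000,000 subjects per scenario. Each cell gives % better / % worse / net; nets come from unrounded values.

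| b (mmHg) | Mean 65 | Mean 70 |
|---|---|---|
| −6 | 50.5 / 3.7 / +46.8 | 45.8 / 3.3 / +42.5 |
| −4 | 38.8 / 6.9 / +31.9 | 34.3 / 6.1 / +28.2 |
| −2 | 27.8 / 11.8 / +15.9 | 23.9 / 10.1 / +13.8 |
| 0 | 18.5 / 18.5 / 0 | 15.4 / 15.4 / 0 |
| +2 | 11.3 / 26.6 / −15.3 | 9.1 / 21.7 / −12.5 |
| +4 | 6.3 / 35.5 / −29.2 | 5.0 / 28.2 / −23.2 |
| +6 | 3.2 / 44.3 / −41.1 | 2.4 / 34.4 / −32.0 |

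These apply to capillary-screened subjects; the figure for a whole arm is s × net. At b = −4 and mean 65 it is 0.10 × 31.9 = 3.2, 0.30 × 31.9 = 9.6 and 0.50 × 31.9 = 16.0 points.

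*Percentage with DSS 1 or 2.* The model gives 1 − Φ((70 − mean − b)/√(9² + 4²)), with √97 = 9.85.

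- Mean 65: b = 0 gives 1 − Φ(5/9.85) = 30.6%; b = −4 gives 1 − Φ(9/9.85) = 18.0%. Spurious rise: 12.6 points.
- Mean 70: 50.0% against 34.2%. Spurious rise: 15.8 points.
- With b = +4 the same quantity falls by 15.4 points (46.0% against 30.6%) and 15.8 points (65.8% against 50.0%).

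*Between arms.* With mean 67, b = −4 and two arms of 45, both arms show the same net shift: about 3, 9 and 15 points at s = 10%, 30% and 50%. The mean difference between arms is −0.03 to +0.03 points. Chance imbalance in capillary share has SD √(2s(1 − s)/45), which is 6.3, 9.7 and 10.5 points. At s = 30% the net shift per capillary subject is 9.15/0.30 = 30.5 points, so imbalance adds noise with SD of about 0.097 × 30.5 = 3.0 points.

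*Subgroup labels.* An offset of 2 to 4 mmHg in either direction moves 13% to 35% of capillary-screened subjects to another class.

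*With an arterial Baseline PaO₂ as the first value,* the model's net shift is zero at every b. The 15% to 18% moving each way at b = 0 is ordinary scatter, and it remains.

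**The case against.** **A reader might infer that sample type is confounded with treatment effect.** The documents do not support that. Sample type at Screening is site practice, fixed before a randomised, double-blind assignment, so every arm is affected alike in expectation. Centre is not a stratification factor (SAP 5.7), which leaves chance imbalance: noise, not bias.

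**A reader might infer that subgroup treatment effects are biased.** They are not. A single label set before treatment involves no comparison of Screening with Week 24, and any misclassification is unrelated to arm. SAP Table 2 does not even say that Screening DSS is used, and Protocol 12.1.3 plans no interaction tests.

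**A reader might expect spurious improvement in particular.** That presumes capillary PaO₂ reads low, which the documents do not state. Reversing the sign reverses the result.

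**The SAP wording might already allow the Baseline gas.** It does mention Baseline, but the table titles, the endpoint and the visit schedule all point to Screening. At best the text is ambiguous.

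**A lavage before randomisation might make Screening DSS out of date.** The pre-version 4.0 stratum, whether "WLL was conducted between the screening visit and the randomization visit", shows that this was possible for early subjects. The number is not given, and the current protocol excludes lavage within one month of Baseline (8.3), with Screening 14 ± 7 days before it. I place no weight on this.

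**Consequence is low.** This stands. DSS is exploratory and descriptive. PaO₂ itself is analysed at Week 24 in SAP 5.3.7, both as relative change and as a responder outcome, from the two visits where arterial sampling is mandatory.

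**Replacing Screening DSS outright would do harm.** This also stands. It would demote a protocol-defined endpoint. If carried into follow-up, where capillary sampling is allowed, it would turn some capillary-to-capillary pairs into arterial-to-capillary ones.

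**Conclusion.** The mismatch is a fact of the documents for subjects whose Screening gas was capillary. It affects the within-arm DSS shift tables and the within-arm change in the percentage with DSS 1 or 2, and it can blur the severity labels if Screening DSS defines them. The comparison between arms is not biased in expectation, and no confirmatory result depends on it. For the percentage with DSS 1 or 2 this follows directly, because the Screening percentage has the same expectation in every arm. For the net shift the simulation, with no true change, agrees.

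Size and direction are unknown. Under the assumptions above, an offset of 4 mmHg gives a net spurious shift of 23 to 32 points in absolute size among capillary-screened subjects, or about 2 to 16 points per arm at capillary shares of 10% to 50%. With no offset it is zero. The assumed distribution also matters: in a variant with PaO₂ truncated below 75 mmHg and no error at Week 24, capillary 4 mmHg low gave 41% to 44% improving, against 35% to 39% without the truncation.

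This is a cheap improvement, not a flaw in the trial's main conclusions.

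**What to change.** 1. **SAP 5.3.8, double-blind period.** Derive an additional pre-treatment DSS from the arterial Baseline (Visit 2) PaO₂, using symptom status from Screening to separate class 1 from class 2. Present the shift tables and the DSS 1 or 2 percentages on these arterial-to-arterial pairs, alongside the protocol-defined Screening-to-Week 24 tables, which stay.
2. **SAP 5.8, Table 2.** Name the Baseline-derived DSS as the severity subgroup variable.
3. **Fallback values.** SAP 5.3.2 lets a Screening value replace a missing Baseline value. Flag any Baseline PaO₂ obtained this way, since it may be capillary.
4. **Follow-up.** Show follow-up DSS also for arterial samples only, as SAP 5.3.8 already does for (A-a)DO₂. That existing summary implies that sample type can be identified in the data. Do not carry the Baseline-derived score into follow-up comparisons with capillary values.

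Cost: one derived variable, a few added tables and some SAP wording; no new data. The downside is that symptom status is carried over about two weeks, from Screening to Baseline. This affects only the split between classes 1 and 2, not the combined DSS 1 or 2 percentage.
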